1.4 Time points and visit windows

All data will be accepted for the analysis. Deviations from the scheduled assessment times are expected to be small and few. The following are the acceptable time windows.

| Day#/Visit# | Activity | Time window |
|--------------------|-----------------|------------------------|
| Day 1 (AM)/Visit 2 | Wash procedures | At least 3 hours apart |
| Day 1 (PM)/Visit 2 | Wash procedures | At least 3 hours apart |
| Day 2 (AM)/Visit 3 | Wash procedures | At least 3 hours apart |

| | | | |
|------------------|--|---------------------|----------------------|
| Document Name | gsk-207619-reporting-and-analysis-plan.pdf | | |
| Type | Version | Document Identifier | Effective Date |
| eldo_controlled | 1.0; CURRENT; Most-Recent; Effective | 090032d580e0a875 | 06-Apr-2018 06:53:51 |
| Reason For Issue | Auto Issue | | |

| Day#/Visit# | Activity | Time window |
|--------------------|-----------------|------------------------|
| Day 2 (PM)/Visit 3 | Wash procedures | At least 3 hours apart |
| Day 3 (AM)/Visit 4 | Wash procedures | At least 3 hours apart |
| Day 3 (PM)/Visit 4 | Wash procedures | At least 3 hours apart |
| Day 4 (AM)/Visit 5 | Wash procedures | At least 3 hours apart |
| Day 4 (PM)/Visit 5 | Wash procedures | At least 3 hours apart |
| Day 5 (AM)/Visit 6 | Wash procedures | At least 3 hours apart |

During screening subjects will sign an informed consent document and then a dermatological assessment will be conducted to ensure subjects have no dermatological conditions on their forearms that might impact subject safety or study results and to ensure subjects are classified as Fitzpatrick Phototype I to IV. A trained, blinded examiner will assess the dryness and redness of each volar forearm and only subjects with a score of zero for dryness and zero for redness will be enrolled into the study. Each subject's medical and medication history will be reviewed, in addition to the inclusion/exclusion criteria. Subsequently, site staff will review lifestyle guidelines and directions with eligible subjects.

A standard soap to be used in place of subjects' normal cleansers will be provided for use during the washout period and study treatment phase. Subjects will be instructed to avoid using any products, including the supplied cleanser, on their forearms throughout the washout and study treatment phase.

Consented eligible subjects will undergo a one-week washout period (5-7 days) prior to first wash procedure, during which the use of any skin cleansing products, including the standard soap, and any other topical products on the forearms will be prohibited.

On Day 1 (Visit 2, AM), eligible subjects will return to the study site and another dermatological assessment will be conducted, as will a review of any concomitant medications used since screening to ensure subject continued eligibility. Compliance concerning correct use of the standard soap will also be checked. Each subject will have two test sites (3x3 cm) marked out on each volar forearm. The distance between the two sites should be at least 1 cm to prevent either the test product, positive control product (Imperial Leather Original bar soap) or negative control (sterile water) applications from spreading over and influencing neighbouring test sites. A trained, blinded examiner assessment (Baseline; Day 1 - AM) of dryness and redness will be conducted at each marked site to ensure the dryness score is zero and the redness score is zero for each site for continued eligibility. The site on each forearm for each wash procedure (or unwashed) will be determined according to the provided randomisation schedule.

| | | | |
|-------------------------|--|----------------------------|-----------------------|
| Document Name | gsk-207619-reporting-and-analysis-plan.pdf | | |
| Type | Version | Document Identifier | Effective Date |
| elido_controlled | 1.0; CURRENT; Most-Recent; Effective | 090032d580e0a875 | 06-Apr-2018 06:53:51 |
| Reason For Issue | Auto Issue | | |

The randomisation schedule will determine the allocation of the 4 test sites for the test product, positive control and negative control wash applications and the site to be left unwashed. A trained technician will perform product application to ensure consistency and eliminate the risk of cross contamination of the study test sites.

Subjects will be acclimatised to the environment of a temperature (20-22°C) and humidity (40-60% RH) controlled room for a period of at least 30 minutes before instrumental measurements of TEWL and corneometry at Baseline (Day 1 - AM) are taken, prior to any wash procedures and additionally at the final visit (Day 5 - PM) following the final wash procedure (Day 5 – AM). (EEMCO, 1997).

The treatment period will consist of 5 days of FCAT wash procedure where subjects will be instructed to come to the site for two wash procedures per day for the first 4 days (AM and PM) and one wash procedure on Day 5 (AM only). Each wash procedure will consist of two washings of each test site AM and PM. The AM and PM wash procedures on any given day will be separated by a minimum of 3 hours.

Further visual assessments of dryness and redness will be performed prior to each PM wash procedure on Days 1 to 4 and again at Day 5 (PM) following the final Day 5AM wash procedure (Appendix 2). The visual assessments of dryness and redness will be performed prior to subject acclimatisation, TEWL and Corneometry measurements on Day 1 and Day 5.

The FCAT generally produces only mild to moderate skin irritation, however, if any site reaches a dryness or redness score of ≥ 5.0 at any time during the study, treatment of all sites on that subject will be immediately discontinued, all test sites will be scored and these will be recorded as an Adverse Event and the subject will be withdrawn from the study.

2 Data analysis

Data analysis will be performed by Biostatistics Division in inVentiv International Pharma Services. Prior to database closure a Blind Data Review Meeting (BDRM) will be conducted in which various aspects of the trial will be discussed and agreed. The statistical analysis software used will be SAS Studio version 9.4 in a WINDOWS environment.

Except as described below, all listings will be produced for all randomised subjects.

2.1 Populations for analysis

Tables described in this section will be produced for all randomised subjects unless it is not mentioned otherwise in the specified sub-section.

2.1.1 Subject disposition

Subject disposition will be summarized as the number and percentage of subjects who complete the study, with the number who discontinue broken down by reason for discontinuation ([Table 14.1.1](#)) using all screened subjects.

| | | | |
|------------------|--|---------------------|----------------------|
| Document Name | gsk-207619-reporting-and-analysis-plan.pdf | | |
| Type | Version | Document Identifier | Effective Date |
| eldo_controlled | 1.0; CURRENT; Most-Recent; Effective | 090032d580e0a875 | 06-Apr-2018 06:53:51 |
| Reason For Issue | Auto Issue | | |

GSK Consumer Healthcare

Confidential

Page 15

Statistical Analysis Plan

207619

2.1.2 Protocol Deviations

Important protocol violations (including violations related to study inclusion/exclusion criteria, conduct of the trial, patient management or patient assessment) will be summarised and listed.

Protocol violations will be tracked by the study team throughout the conduct of the study. Data will be reviewed prior to un-blinding and closure of the database to ensure all important violations are captured and categorised.

Major violations of the protocol procedures identified as liable to influence the efficacy outcome are as follows:

All-important violations will be defined in the “Review Listing Requirement (RLR)” document.

A list of protocol deviation will be listed in [Listing 16.2.2](#).

2.1.3 Analysis populations

Four analysis populations are defined.

| Population | Definition / Criteria | Analyses Evaluated |
|-----------------------|--|--|
| All Screened Subjects | 
 All subjects those who are screened | 
 Disposition |
| Randomised | 
 Randomised population will include all subjects who may or may not receive the any wash procedure. | 
 Protocol violation |
| Safety | 
 Safety population includes all subjects who received at least one wash procedure. | 
 Safety Analyses |
| Intent-to-Treat (ITT) | 
 The ‘Intent to treat’ (ITT) population includes all subjects who are randomised, receive at least one wash procedure, including sterile water, and have at least one post-baseline assessment available. | 
 Efficacy analysis (Dryness, Redness, etc.) |

2.1.4 Subgroups/Stratifications

Not Applicable.

2.1.5 Centres pools

Not Applicable.

2.2 Patient demographics/other Baseline characteristics

Demographic and baseline characteristics summaries will be produced for the safety and ITT.

2.2.1 Demographic and Baseline characteristics

Categorical demographic variables include gender, race and Fitzpatrick scale. These variables will be summarized by the number and percentage of subjects with each relevant characteristic

| | | | |
|------------------|--|---------------------|----------------------|
| Document Name | gsk-207619-reporting-and-analysis-plan.pdf | | |
| Type | Version | Document Identifier | Effective Date |
| eldo_controlled | 1.0; CURRENT; Most-Recent; Effective | 090032d580e0a875 | 06-Apr-2018 06:53:51 |
| Reason For Issue | Auto Issue | | |

GSK Consumer Healthcare

Confidential

Page 16

Statistical Analysis Plan

207619

(Table 14.1.4.1 and Table 14.1.4.2). Age will be summarized by the number of non-missing observations, mean, and standard deviation, median, minimum and maximum values.

The Fitzpatrick scale is a numerical classification that is widely used by dermatologists to classify a person's skin type by their response to the sun exposure (Fitzpatrick, 1988).

CCI

2.2.2 General medical history

Medical history data will not be presented in the study report. A data listing will be produced for evaluation of protocol violations only at the blinded data review stage.

2.2.3 Characteristics of Disease

Not Applicable.

2.3 Treatments (study treatment, other concomitant therapies, compliance)

Compliance data will be summarized for the ITT population. Exposure and other medications will be summarized on the safety population.

2.3.1 Study Product/treatment Compliance and Exposure

Not Applicable.

2.3.2 Any protocol deviation associated with bar soap wash adherence will be listed at the blinded data review stage. Concomitant medication

Concomitant medication/non-drug treatments data will not be presented in the study report. A data listing will be produced for evaluation of protocol violations only at the blinded data review stage.

2.4 Analysis of dermal response

2.4.1 Primary dermal response endpoint

2.4.1.1 Primary dermal response endpoint definition

| | | | |
|------------------|--|---------------------|----------------------|
| Document Name | gsk-207619-reporting-and-analysis-plan.pdf | | |
| Type | Version | Document Identifier | Effective Date |
| eldo_controlled | 1.0; CURRENT; Most-Recent; Effective | 090032d580e0a875 | 06-Apr-2018 06:53:51 |
| Reason For Issue | Auto Issue | | |

GSK Consumer Healthcare

Confidential

Page 17

Statistical Analysis Plan

207619

The primary analysis will be performed to compare change from baseline in examiner rating of dryness to 3 hours following last wash procedure on day 5 for the test product versus water in the skin of healthy subjects. Analyses will be performed on the ITT population.

The forearm grading scale is described below –

Forearm Grading Scale:

Any skin response at any of the wash procedure areas on the volar forearm will be clinically assessed using the criteria recommended by Lukacovic, 1987. The following grades will be used to express the response observed at the time of examination:

CCI

CCI

| | | | |
|------------------|--|---------------------|----------------------|
| Document Name | gsk-207619-reporting-and-analysis-plan.pdf | | |
| Type | Version | Document Identifier | Effective Date |
| elido_controlled | 1.0; CURRENT; Most-Recent; Effective | 090032d580e0a875 | 06-Apr-2018 06:53:51 |
| Reason For Issue | Auto Issue | | |

CCI

Individual subjects observations for dryness and redness scores, TEWL and corneometer will be listed by visit and treatment ([Listing 16.2.6](#)).

Frequency table of dryness and redness score measurements at each time point will be presented based of ITT population ([Table 14.2.1.1, 14.2.1.2](#)). Separate summary statistics table (displaying number of non-missing observations, mean, standard deviation, median, minimum, and maximum) of the raw and change from baseline in dryness and redness scores, TEWL and corneometer measurements at each visit will be summarized for test product, water, positive control and unwashed site ([Table 14.2.1.3, 14.2.1.4, 14.2.1.5 and 14.2.1.6](#)) using ITT population.

2.4.1.2 Statistical hypothesis, model, and method of analysis

The primary endpoint will be tested for the non-inferiority of the test product to water in change from baseline on day 5 in examiner rating of dryness.

The null and alternative hypotheses for the testing of non-inferiority will be following –

| | |
|--|--|
| Null Hypothesis (H_0): | The population mean of dryness (in the examiner rating scale) for test product minus the population mean of dryness (in the examiner rating scale) for water ≥ 0.25 |
| Alternative Hypothesis (H_{a1}): | The population mean of dryness (in the examiner rating scale) for test product minus the population mean of dryness (in the examiner rating scale) for water < 0.25 |

To test the above mentioned hypotheses an ~~Analysis of Covariance (ANCOVA)~~ Analysis of Variance (ANOVA) model or appropriate statistical method will be used. The change from baseline in examiner rating of dryness to 3 hours following last wash procedure on day 5 will be considered as the response variable. The model will include treatment and site as fixed effects; ~~baseline examiner rating of dryness as a covariate~~ and subject as a random effect.

Least Square Means (LSMeans) for each treatment will be presented. The treatment difference estimates (test product to water), and upper one-sided 90% confidence limit will be presented. If the upper one-sided 90% confidence limit is less than 0.25 it will be concluded that the test product is not inferior to the water in the examiner rating of dryness ([Table 14.2.2.1](#)). If the assumptions underlying the model are strained due to the ordinal nature of the response distribution (or other issues) suitable alternatives may be sought to support the ANCOVA findings.

| | | | |
|------------------|--|---------------------|----------------------|
| Document Name | gsk-207619-reporting-and-analysis-plan.pdf | | |
| Type | Version | Document Identifier | Effective Date |
| eldo_controlled | 1.0; CURRENT; Most-Recent; Effective | 090032d580e0a875 | 06-Apr-2018 06:53:51 |
| Reason For Issue | Auto Issue | | |

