## 9.2. General Considerations

The test for non-inferiority between test product versus water in the examiner rating of dryness and redness will be one-sided at the 0.05 level of significance. All other statistical tests will be done at a two-sided 0.05 level of significance.

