### 9.2.3. Criteria for Evaluation

The primary endpoint will be tested for non-inferiority of the test product to water in examiner rating of dryness. The test will be carried out as follows: within subject treatment difference (test to water) in change from Baseline to 3 hr following last application on Day 5 will be estimated. To test the hypothesis that the difference has a mean 0.25 or greater at 0.05 level of significance, a one-sided upper 95% confidence limit will be estimated for the test product to water mean difference. If the upper 95% confidence limit is below 0.25, it will be concluded that the test product is not inferior to water in the examiner rating of dryness.

The criteria for non-inferiority of 0.25 on mean dryness score is considered clinically relevant after consideration of mean differences seen between positive control (bar soap) and water in previous studies (Ertel, 1995 and GSK Clinical Study CCI [REDACTED])

Document Name	GSK201701001001		
Type	Version	Document Identifier	Effective Date
elido_clinicalelbc	1.0; CURRENT; Most-Recent; Effective	090032d580d0a8784	06-Mar-2018 07:52:18
Reason For Issue	Auto Issue		

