### 9.3.2. Primary Analysis(es)

The primary endpoint will be tested for non-inferiority of the test product to water in change from baseline on Day 5 in examiner rating of dryness, using treatment estimates derived from an ANCOVA with subject (random effect), treatment and site as factors with baseline value as a covariate. The LSMeans will be presented for each treatment. The treatment difference (test product to water) and upper one-sided 95% confidence limit will be presented. If this upper confidence limit is below 0.25, it will be concluded that the test product is not inferior to water in the examiner rating of dryness.

This will be corroborated by using a one-sided 0.05 level of significance Wilcoxon sign rank test performed on the adjusted difference (within subject change from Baseline subtracted by 0.25) on Day 5 to test the hypothesis that the mean change from baseline for the test product is not greater than the change for water by 0.25 or more. The interpretation of this analysis will be assessed with caution as the non-

Document Name	GSK2017010007013		
Type	Version	Document Identifier	Effective Date
elido_clinicalelbc	1.0; CURRENT; Most-Recent; Effective	090032d580d0a8784	06-Mar-2018 06:52:18
Reason For Issue	Auto Issue		

inferiority margin of 0.25 is based on mean dryness score with assumption of normal rather than discreet distribution.

For individual subjects an increase in dryness score from baseline of 1 or more with treatment is considered as a clinically relevant irritation response, so additional analysis will be performed based on subjects with this response, with more details provided in the SAP.

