2.5 Analysis of secondary objectives

2.5.1 Dermal Response (secondary)

The first secondary endpoint will be tested for the non-inferiority of the test product to water in change from baseline on day 5 in examiner rating of redness.

| | | | |
|------------------|--|---------------------|----------------------|
| Document Name | gsk-207619-reporting-and-analysis-plan.pdf | | |
| Type | Version | Document Identifier | Effective Date |
| eldo_controlled | 1.0; CURRENT; Most-Recent; Effective | 090032d580e0a875 | 06-Apr-2018 06:53:51 |
| Reason For Issue | Auto Issue | | |

GSK Consumer Healthcare

Confidential

Page 20

Statistical Analysis Plan

207619

To test the above mentioned hypotheses an Analysis of Covariance Variance (ANOVA) (ANCOVA) model will be used. The change from baseline in examiner rating of redness to 3 hours following last wash procedure on day 5 will be considered as the response variable. The model will include treatment and site as fixed effects; ~~baseline examiner rating of redness as a covariate~~ and subject as a random effect.

Least Square Means (LSMeans) for each treatment will be presented. The treatment difference estimates (test product to water), upper one-sided 90% confidence limit will be presented. If the upper one-sided 90% confidence limit is less than 0.25 it will be concluded that the test product is not inferior to the water in the examiner rating of redness ([Table 14.2.2.3](#)).

Second, secondary endpoint examiner assessment of dryness ([Table 14.2.2.4](#)) and redness ([Table 14.2.2.5](#)) at day 2,3,4, and 5, 3 hour post last wash procedure will be analyzed using ANCOVA ANOVA model for both dryness and redness separately. The model will be same as mentioned for the primary and first secondary efficacy endpoint analyses. Adjusted means, 95% CI and p-values will be provided for the following treatment comparison.

- Positive Control versus water
- Positive Control versus test product
- Water versus un-washed area

Change from baseline in TEWL ([Table 14.2.3.1](#)) measurement and Corneometer measurement ([Table 14.2.3.2](#)) will be analysed using the ANCOVA model with treatment and site as fixed effect; baseline corresponding measurements as a covariate and subject as a random effect. The adjusted means, treatment differences, 95% CI and p-values will be presented for the following comparisons.

- Test product versus water
- Positive Control versus water
- Positive Control versus test product

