2.8 Sample size calculation

The primary hypothesis is that the test product is not inferior to water in the change from baseline in the examiner rating of dryness on Day 5. Assuming that the standard deviation of the within subject treatment difference in change from baseline in examiner rating of dryness is 0.25 (based on previous study GSKCH: [CCI](#)

[REDACTED]

[REDACTED]

[REDACTED]

A sufficient number of subjects will be screened in order to randomise 45 subjects and to ensure that at least 40 subjects complete the study.

3 Changes to the Protocol Defined Statistical Analysis Plan

~~There were no changes or deviations to the originally planned statistical analysis specified in the [protocol version 1.0](#)~~ The use of the Wilcoxon type test in support of the primary was removed due to limitations of that approach. Any potential supportive analysis will be considered if the ANOVA assumptions are strained. [protocol version 1.0](#) [(Dated: 06/MAR/2017)].

| | | | |
|------------------|--|---------------------|----------------------|
| Document Name | gsk-207619-reporting-and-analysis-plan.pdf | | |
| Type | Version | Document Identifier | Effective Date |
| eldo_controlled | 1.0; CURRENT; Most-Recent; Effective | 090032d580e0a875 | 06-Apr-2018 06:53:51 |
| Reason For Issue | Auto Issue | | |

4 Appendix 1:

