| Minimum | —** | | —** | | —** | | —** | | |
| Maximum | —** | | —** | | —** | | —** | | |

Page x of y

PPD

Programming Note:

- Repeat for Day 5
- Also, for the corneometer assessment

| | | | |
|------------------|--|---------------------|----------------------|
| Document Name | gsk-207619-reporting-and-analysis-plan.pdf | | |
| Type | Version | Document Identifier | Effective Date |
| eldo_controlled | 1.0; CURRENT; Most-Recent; Effective | 090032d580e0a875 | 06-Apr-2018 06:53:51 |
| Reason For Issue | Auto Issue | | |

Protocol: 207619

Program Run Date:ddmonyyyy

Table 14.2.2.1
Statistical Analysis of Examiner Assessment of Dryness on Day 5, 3 Hour Post Last Wash Procedure
Intent to Treat Population

Intent to Treat Population N=XX)

| | Micellar cleanser | | Baxter Sterile Water | |
|---|-------------------|------------------------|----------------------|--------------|
| | (N = xx) | | (N = xx) | |
| | Baseline [1] | Change | Baseline [1] | Change |
| Day 5, 3 hour post last wash | | | | |
| n | xx | xx | xx | xx |
| Missing | xx | xx | xx | xx |
| Mean | xx.x | xx.x | xx.x | xx.x |
| SD | xx.xx | xx.xx | xx.xx | xx.xx |
| SE | xx.xx | xx.xx | xx.xx | xx.xx |
| Median | xx.x | xx.x | xx.x | xx.x |
| Minimum | xx | xx | xx | xx |
| Maximum | xx | xx | xx | xx |
| Adjusted Mean (SE) [2] | | xx.x (xx.xx) | | xx.x (xx.xx) |
| 90% CI [2] | | (xx.x, xx.x) | | (xx.x, xx.x) |
| P-value [2] | | 0.xxxx | | 0.xxxx |
| Comparison Between Treatments | Difference [2,3] | Upper One-sided 90% CI | P-value | |
| Micellar cleanser vs Baxter Sterile Water | xx.x | (xx.x, xx.x) | 0.xxxx | |

[1] Baseline visit is day 1(AM) visit 2 assessment. Baseline only includes those subjects who have a corresponding post-baseline assessment.

[2] From ANOVA model with change from baseline in examiner assessment on dryness as response and treatment, site as fixed effects. If one-sided upper 95% CI is less than 0.25 then non-inferiority is established.

[3] Difference is first named treatment minus second named treatment such that a negative difference favours first named treatment.

[4] P-value from Wilcoxon sign rank test, which is based on the adjusted differences. Adjusted difference is calculated in the following manner;

Page x of y

PPD

Protocol: 207619

Program Run Date:ddmonyyyy

| | | | | | | | | | | | | |
|------------------|--|--|--|--|--|--|--|--|--|--|--|--|
| Document Name | gsk-207619-reporting-and-analysis-plan.pdf | | | | | | | | | | | |

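### The SAP judges non-inferiority on a one-sided 90% limit where the protocol requires a one-sided 95% limit, which doubles the false-positive rate from 5% to 10%

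*SAP*

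**What the plan says.** **Protocol.** Section 9.2 says that the comparison of test product with water "in the examiner rating of dryness and redness will be one-sided at the 0.05 level of significance". Section 9.2.3 gives the matching decision rule: "If the upper 95% confidence limit is below 0.25, it will be concluded that the test product is not inferior to water". Section 9.3.2 repeats the level for the primary analysis: "The treatment difference (test product to water) and upper one-sided 95% confidence limit will be presented". The synopsis agrees.

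**SAP text.** For dryness on Day 5, the amended section 2.4.1.2 says: "If the upper one-sided 90% confidence limit is less than 0.25 it will be concluded that the test product is not inferior". For redness, section 2.5.1 applies the same criterion: "upper one-sided 90% confidence limit is less than 0.25 it will be concluded that the test product is not inferior to the water". The 90% wording was already in the SAP before its amendment. The amendment replaced ANCOVA with ANOVA in these sections and left the confidence level as it was.

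**SAP table shell.** In the amended shell for Table 14.2.2.1, the column for the treatment comparison is headed as an upper one-sided 90% interval. Footnote [2] of the same shell says: "If one-sided upper 95% CI is less than 0.25 then non-inferiority is established". The redness table (14.2.2.2) is built from this shell.

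**Declared changes.** SAP section 3 names one departure from the protocol analysis: "The use of the Wilcoxon type test in support of the primary was removed due to limitations of that approach". It says nothing about the confidence level.

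**The concern.** The confidence level sets the pass/fail threshold for the primary conclusion and the first secondary conclusion. The protocol fixes it at one-sided 0.05. Followed as written, the SAP tests at one-sided 0.10, and it neither states nor justifies a change.

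Two things are at stake. First, the SAP text accepts a product lying exactly at the margin twice as often as the protocol allows. Second, a programmer working from the SAP text and one working from the shell's footnote could reach opposite verdicts on the same data, and no rule says which takes precedence.

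**Working it through.** **Inputs**
- Margin: 0.25 (protocol 9.2.3; SAP 2.4.1.2).
- SD of the within-subject treatment difference in change from baseline: 0.25 (protocol 9.1; SAP 2.8).
- Subjects: 45 randomised, at least 40 completing (protocol 9.1).
- Levels compared: one-sided 95% (protocol) and one-sided 90% (SAP text).

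**Step 1: significance level of each rule.** If non-inferiority is concluded when an upper one-sided limit with coverage 1 − a falls below the margin, the false-positive rate at a true difference equal to the margin is a.
- Protocol: 1 − 0.95 = 0.05. This reproduces the level stated in protocol 9.2.
- SAP text: 1 − 0.90 = 0.10.

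The ratio is 2, whatever the SD or sample size. A simulation of 400,000 paired samples at n = 40 and a true difference of 0.25 gave 0.049 and 0.099.

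**Step 2: largest observed difference that passes.** I use a paired t with n = 40 as an approximation to the planned model. The standard error is 0.25/√40 = 0.0395.
- One-sided 95%: t(0.95, 39) = 1.685; half-width 1.685 × 0.0395 = 0.0666; limit 0.25 − 0.0666 = 0.183.
- One-sided 90%: t(0.90, 39) = 1.304; half-width 1.304 × 0.0395 = 0.0515; limit 0.25 − 0.0515 = 0.198 (0.19847 unrounded).

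An observed difference between these two values fails under the protocol rule and passes under the SAP rule. With 45 subjects the zone is 0.187 to 0.202.

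The planned model fits four treatments and four sites within subject, giving 159 − 39 − 3 − 3 = 114 residual degrees of freedom at n = 40. With the same standard error, the zone becomes 0.184 to 0.199, so the approximation matters little.

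**Step 3: chance of passing.** From the noncentral t with 39 df and noncentrality (δ − 0.25)/0.0395, where δ is the true excess dryness over water:

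| True excess δ | One-sided 95% rule | One-sided 90% rule |
|---|---|---|
| 0.00 | about 100% | about 100% |
| 0.10 | 98.1% | 99.3% |
| 0.15 | 80.0% | 88.9% |
| 0.18 | 54% | 68% |
| 0.20 | 34% | 49% |
| 0.25 (margin) | 5% | 10% |

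**Step 4: a possible source.** The upper end of a two-sided 90% interval uses z = 1.645, the same multiplier as a one-sided 95% limit. A one-sided 90% limit uses z = 1.282. Labelling a two-sided 90% interval as one-sided would turn the protocol's rule into the one the SAP states.

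**The case against.** The strongest reply is that nobody chose a 10% test. On this view the 90% is the upper end of a two-sided 90% interval, the error rate stays at 5%, and only the label is wrong. The shell supports this. The cell under the one-sided heading has two ends, although a one-sided limit is a single number; the adjusted-mean row also shows a two-ended 90% interval; and footnote [2] keeps the 95% criterion. Before its amendment the SAP already contained the 90% wording, yet it declared no change from the protocol.

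This is probably the right account of how the error arose, and nothing shows a deliberate move to 0.10. It does not settle the rule, however. Both SAP sections say one-sided when they state the criterion, and an analyst following them would compute the z = 1.282 bound.

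Three smaller points stand:
- The silence of SAP section 3 is weak evidence of intent, because that section also fails to spell out the switch from ANCOVA to ANOVA.
- The sample size cannot show which level was meant. The power and assumed true difference are redacted, and with 40 completers 80% power at 0.05 and 90% power at 0.10 both occur at a true excess of about 0.15.
- If the cleanser is truly no more drying than water, both rules pass almost surely. The verdict differs only in a narrow band of observed differences.

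**Conclusion.** The concern holds. The protocol states a one-sided 0.05 test consistently. The SAP text states a one-sided 0.10 test for dryness and redness, and its primary table shell states both levels.

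The doubling from 5% to 10% follows from the SAP wording read literally and needs no assumption about SD or sample size. The disputed zone of 0.183 to 0.198 and the pass rates (34% against 49% at a true excess of 0.20, 54% against 68% at 0.18) rest on the planned SD of 0.25, 40 completers and a paired t approximation. If a two-sided 90% interval was meant, the intended error rate is still 5%, but the written rule for the primary conclusion is wrong and must be corrected before anyone applies it.

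**What to change.** - **SAP 2.4.1.2 and 2.5.1:** base the decision on the upper one-sided 95% confidence limit, and add that it equals the upper limit of the two-sided 90% interval.
- **Table 14.2.2.1 shell, and Table 14.2.2.2 built from it:** make the comparison heading agree with footnote [2]. Print either a single one-sided 95% upper limit or a two-sided 90% interval labelled as such. Label the adjusted-mean row as two-sided.
- **Table 14.2.2.3 footnote [2]:** remove the non-inferiority criterion, or confine it to cleanser versus water on Day 5. That table reports two-sided 95% intervals for several days and comparisons.
- **If 0.10 was intended:** declare and justify it in SAP section 3, and reconcile it with the protocol, before unblinding.

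The cost is SAP wording and shell edits only, with no change to design, sample size or data collection. The decision becomes slightly stricter than the current SAP text and returns to the level in the protocol.
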